TXA Study Plan

Title:

Prevention of Postpartum Hemorrhage with Intravenous Tranexamic Acid (PPHIT)

Background:

Hemorrhage remains the leading cause of maternal mortality worldwide. In 2014, in a systematic analysis of the causes of maternal death, the WHO noted that even in the face of interventions developed to actively manage the third stage of labor, 27.1% of maternal deaths were directly attributable to excessive blood loss.¹

Risk factors for postpartum hemorrhage (PPH) have been identified, but the majority of cases occur in low risk women.^{2,3} As such, the routine use of Pitocin or oxytocin in the third stage of labor is recommended in all women, and has been well documented to reduce the risk of excessive blood loss.^{2,3} Uterotonics such as methylergonovine, 15-methyl prostaglandin F_{2α} and misoprostol have shown to be particularly useful adjuncts as decreased uterine tone is the most common etiology of blood loss.² More recently, tranexamic acid (TXA) has been shown to be efficacious in the prevention of postpartum hemorrhage in certain cohorts.^{3,4}

Tranexamic acid exerts its effect through the binding of plasmin and subsequent inhibition of fibrin degradation. It is regarded as pregnancy category B by the Food and Drug Administration (FDA). In 2015, a meta-analysis of 11 randomized controlled trials (RCTs) evaluated the efficacy of TXA on operative blood loss when given prior to cesarean delivery. Women who received TXA had lower rates of hemorrhage, as well as, significantly less need for blood transfusion.⁵ A similarly designed meta-analysis (9 RCTs) that same year done by Simonazzi et al reached the same conclusions. This study also noted that the use of uterotonics was significantly reduced in the TXA group.⁶

Other reviews however, do not echo these sentiments, stating that given the size and large range in the design of the studies that the data is insufficient to allow for the recommendation of widespread use of TXA. These reviews included in their analysis the use of TXA in response to PPH.^{3,4} A larger systematic analysis was then carried out on trials evaluating the prophylactic use of TXA in cesarean deliveries and in response to hemorrhage in vaginal deliveries. A meta-analysis was planned, but not carried out, as the authors found the 26 trials to be small, of poor quality, and with flawed design. They concluded that because of this, there was no reliable evidence that TXA prevents PPH.⁷

9. WHO Recommendations for the Prevention and Treatment of Postpartum Haemorrhage. Geneva: World Health Organization; 2012.
10. WOMAN Trial Collaborators. Effect of early tranexamic acid administration on mortality, hysterectomy, and other morbidities in women with post-partum haemorrhage (WOMAN): an international, randomised, double-blind, placebo-controlled trial. Lancet. 2017 Apr 26.

Research Design:

a. General Approach: Prospective Cohort study

b. Description: Phase 4

c. Methods: One Arm

d. Statistical Analysis:

- SPSS software will be used for our statistical analysis. Normal distribution will be assumed given the intended number of patients for analysis. Categorical variables will be analyzed using the Chi-square test. The t-test will be utilized for the comparison of continuous interval data.

-Using postpartum hemorrhage rate of 2.86% (institutional data), and a desired impact of reducing the hemorrhage rates by 50% after implementation of the new protocol, then 890 subjects would need to be recruited to answer the question.

e. Safety Analysis Plan:

- Data collection for each participant will occur in real time during pre and post delivery times, therefore safety monitoring of the patient and data will be simultaneous.
- A Research monitor has been appointed to oversee the safe and ethical conduct of the study. Additionally, the Research Monitor will provide review and comment on any adverse events. The Research Monitor is not a member of the investigative team. The role of the Research Monitor is as follows:
 1. monitor the consent process to ensure an absence of coercion
 2. monitor data collection/clinical outcome
 3. review all adverse event reports with comments from the PI and forward to the IRB with his/her own comments. Adverse events must be received by the IRB within 5 business days of occurrence or reporting (within 24 hours for serious adverse events)
 4. ensure the inclusion/exclusion criteria are followed
 5. review data security measures
- Any emerging safety concerns to include any adverse event rate higher than this institution's historical average will result in a halt to the study.

Subject Population:

Pregnant women presenting for delivery at NMCSO

a. Exclusion/Inclusion criteria:

Exclusion:

- a. Age less than 18 years
- b. Planned cesarean hysterectomy
- c. Current anticoagulant use
- d. Subarachnoid hemorrhage
- e. Any active/current intravascular clotting (i.e. venous thromboembolic events)
- f. Patients with a hypersensitivity to TXA or any of the ingredients

- g. History of venous or arterial thrombotic events because use of tranexamic acid is a risk factor for thromboembolism.
- h. Conditions that predispose patients to thromboembolic events (e.g. thrombophilias, autoimmune diseases such as lupus, active cancer, congestive heart failure) because of increased risk of thrombosis
- i. Patients taking factor IX complex concentrates or anti-inhibitor coagulant concentrates (e.g. FEIBA NF)
- j. Seizure disorder because the use of tranexamic acid has been associated with postoperative seizures
- k. Patients with a baseline creatinine 1.2 or higher, history of renal insufficiency, or renal disease because of the risk of toxicity in patients with preexisting disease.
- l. Patients with frank hematuria because ureteral obstruction due to clot formation has been reported in patients with upper urinary tract bleeding who were treated with tranexamic acid
- m. History of retinal disease as cases of central retinal artery and vein obstruction have been reported in patients treated with tranexamic acid
- n. Patients with acquired defective color vision
- o. Patients with retinal diseases; cases of central retinal artery and central retinal vein obstruction have been reported in patients treated with intravenous tranexamic acid.

Inclusion:

-Pregnant women 18-54 years old delivering at Navy Medical Center San Diego (NMCS D)

Recruitment Process:

Patients will be identified in the antenatal clinics of Naval Medical Center San Diego. All patients that meet the inclusion criteria will be offered inclusion in the study.

All English speaking women who are eligible to receive care at NMCS D and presenting to NMCS D's Labor and Delivery Unit, who are at least 18 years old, not older than 54, and who are scheduled to deliver at NMCS D, will be given verbal and/or a written information sheet about the study and a description of what the study entails. OBGYN staff providers and residents will also be given an information sheet about the study. Opportunities for potential participant recruitment include:

- NMCS D Prenatal Registration
- NMCS D Gestational Diabetes education classes
- NMCS D Labor and Delivery tour of the unit

Subject eligibility and screening will take place prior to offering potential subjects the opportunity to participate in the study. An eligibility and screening tool will be used as part of the recruitment process.

Consent Process:

Informed consent will be obtained by members of the research team at any point during the subjects routine prenatal care visits.

Consent will only be obtained during a face-to-face communication in a confidential setting.

A member of the research team will provide a verbal and/or written information sheet giving a complete description of the rationale, goals, and requirements of the study. Participants will also be told of the volunteer nature of the study, and that they may cancel their participation in the study at any time, following the process outlined in the consent form.

The PI, AIs, or the research nurse will be available during the recruitment and enrollment phase of the trial. The PI/AI is available throughout the course of this trial. After reading the consent, having all questions answered to their satisfaction, and acknowledging understanding of what is involved in the trial, participants will be asked to sign the consent, along with the research team member obtaining the consent. A copy of the participant's signed consent will be given to them for their personal records.

All consents will include the participant's signature on the IRB-approved consent form. The participant will be given a copy of their signed consent form.

The original signed consent will be kept by the Clinical Research Nurse Coordinator in a locked cabinet in the office of the Clinical Research Nurse Coordinator.

Participants will be informed that they have the right to withdraw from this study at any time. If they decide to stop taking part in this study, they will be asked to tell the principle investigator as soon as possible.

Subject participation may be stopped without participant consent if remaining in the study might be dangerous or harmful in the investigator's opinion. It may also be stopped without participant consent if the military mission requires it, or if the participant loses the right to receive medical care at a military hospital.

Study Procedures:

1. Recruitment/Enrollment
 1. Identify subjects who meet inclusion criteria at prenatal registration, L&D tours, GDM classes, and on L&D
 2. Obtain written consent from potential participants after participant has had time to read, understand and comprehend
 3. "TXA Study Participant" to be added to problem list on hard chart, AHLTA template and ESSENTRIS intake
2. Implementation on L&D
 1. Re-identify patients on admission
 2. For patients that present for delivery at a gestational age less than 34 weeks, it will be recommended that they discard their breast milk until 24 hours after their last TXA administration.
 3. Order TXA for patient in ESSENTRIS
 4. RN to pull TXA from Pyxis and put in patient's room
 5. TXA per protocol (see supplement A)
 6. The use of additional uterotonics or single additional dose of TXA is at the discretion of the delivering provider
 7. For patient monitoring protocol please see Supplement B.
 8. All neonates are monitored for a minimum of 24 hours either by the NICU or the Newborn Nursery. Vitals are taken every four hours. Weights and bilirubin levels are obtained daily. Daily physical exams are performed.
3. Data collection
 1. Participants will be assigned an individualized subject number upon their enrollment to the study.
 2. Participants will be followed from their enrollment into the study until six weeks postpartum.
 3. An Excel spreadsheet will be used to collect the variables as listed above.
 4. Once the variable collection is complete, the information will become de-identified.

5. Chart review will be performed to estimate institutional rates of the secondary outcomes in the 12 months preceding the initiation of the protocol.
4. Data Analysis
 1. SPSS software will be used for our statistical analysis. Normal distribution will be assumed given the intended number of patients for analysis. Categorical variables will be analyzed using the Chi-square test. The t-test will be utilized for the comparison of continuous interval data.
 2. Using a postpartum hemorrhage rate of 2.86% (institutional data), and a desired impact of reducing the hemorrhage rates by 50% after implementation of the new protocol, then 890 subjects would need to be recruited to answer the question.
 3. The secondary outcomes will also be tested against institutional rates. Institutional rates will be estimated by record sampling done at the time of data collection.

Experimental Procedures:

See supplement A

Research materials collected:

Variables to be collected:

Age, race/ethnicity, DoD status, BMI, gestational age, # of fetuses, gravidity, parity, admission diagnoses, admission estimated fetal weight, intrapartum diagnoses, postpartum diagnoses, misoprostol use, oxytocin use, mechanical dilation, duration of labor, magnesium sulfate use, planned mode of delivery, mode of delivery, birth weight, indication for operative delivery, neonatal outcomes, maternal outcomes, admission to the intensive care unit, uterotonic use, mechanical tamponade, blood product transfusion, estimated blood loss, qualitative blood loss, cumulative blood loss, laboratory results, post-delivery laboratory results

Confounding variables:

Management of the 3rd stage of labor

Source of the data:

Outpatient records (AHLTA), Inpatient records (Essentris). As providers, the investigators have access to these systems as a standard of care for patients receiving care from investigator-providers.

Paper records created in the Labor and Delivery department during the course of a delivery.

The data collected will be measured against the historic PPH rates of NMCSO over a period of time to be determined.

Protection of Privacy:

Each participant will be given a unique study number. A master list with only the minimal Personal Identifiable Information (PII) needed for follow up and their study number will be kept in the PI's office on a CAC PIN protected computer in the PI's locked office. The master list will be used to track the results of the study participant's data collection.

An Excel spread sheet will be used to collect this information using only the participants unique study number and stored electronically on a CAC PIN protected computer in the PI's locked office.

All data and PII will be destroyed (shred or deleted) at the conclusion of this project.

Risks:

Within this study, the use of protected health information (PHI) involves no more than a minimal risk to the privacy of individuals as there is a clear plan to protect the identifiers from improper use and disclosure. All identifiers will remain in the protected medical record and any identifier extracted will be destroyed at the earliest opportunity consistent with conduct of the research, unless there is a health or research justification for retaining the identifiers or such retention is otherwise required by law. PHI will not be reused or disclosed to any other person or entity, except as required by law, for authorized oversight of the research study, or for other research for which the use or disclosure of protected health information would be permitted by approval of the IRB.

We do not anticipate any risk to subjects participating in this study other than those encountered in routine labor and delivery experiences. TXA is being used in the hopes of reducing the amount of bleeding experienced in postpartum hemorrhage events. It will not eliminate all bleeding or need for a transfusion.

Risk/Side effects of TXA:

Contraindications

- Patients with subarachnoid hemorrhage. Anecdotal experience indicates that cerebral edema and cerebral infarction may be caused by TXA in such patients
- Patients with active intravascular clotting (e.g. venous thromboembolic events)
- Patients with hypersensitivity to TXA or any of the ingredients

Precautions

- The dose of TXA should be reduced in patients with renal insufficiency because of the risk of accumulation
- Patients with a previous history of thromboembolic disease may be at increased risk for venous or arterial thrombosis. More specifically, patients with DVT within one year, a hypercoagulable genetic disorder, a history of previous stroke, significant coronary artery disease, cardiac stents requiring ongoing clopidogrel (Plavix) treatment, or unstable angina are likely not appropriate candidates for TXA

Adverse Reactions

- Gastrointestinal disturbances (nausea, vomiting, diarrhea) may occur but disappear when the dosage is reduced
- Allergic dermatitis, giddiness, and hypotension have been reported occasionally
- Hypotension has been observed when intravenous injection is too rapid
- Rare events from worldwide post marketing reports have included thromboembolic events (e.g., deep vein thrombosis, pulmonary embolism, cerebral thrombosis, acute renal cortical necrosis, and central retinal artery and vein obstruction), convulsion, chromatopsia, and visual impairment

Radiation/Laser Exposure: None

Justification/Minimization of Risks:

All identifiers will remain in the protected medical record. Any PHI extracted as a result of this study will be destroyed at the earliest opportunity consistent with conduct of the research, unless there is a health or research justification for retaining the identifiers or such retention is otherwise required by law. Protected health information will not be reused or disclosed to any other person or entity, except as required by law, for authorized oversight of the research study, or for other research for which the use or disclosure of protected health information would be permitted by approval of the IRB.

The current Maternal Child Executive Committee Policy on Tranexamic Acid (TXA) Administration will be followed to minimize any risks of harm to subjects.

Benefits:

Potential benefits of the research to the subject include a reduction in blood loss from delivery, decreased need for uterotonic medications, decreased need for blood transfusion, and less morbidity as a result of symptomatic anemia, resulting in increased satisfaction with the postpartum experience and increased maternal-neonate interactions.

Potential benefits of the research to the community/society included less overall maternal morbidity/mortality as well as a decreased demand on limited resources (i.e. blood products, uterotonic medications, time of additional healthcare providers, etc).

Requirements for Research Monitor:

Research Monitor Responsibilities:

Serves as a medical monitor, reviewing AEs as they are discovered to determine if the events suggest a trend toward increased risk to subjects that would require additional safeguards, subject notifications, or an invoking of stopping rules.

To satisfy these two areas of responsibility, the research monitor may discuss the research protocol with the investigators, interview study subjects, and consult with others outside of the project about the research. In the event a problem is identified, they have authority to stop a research protocol in progress, remove individual subjects from a study, and take whatever steps are necessary to protect the safety and well-being of subjects until the IRB can assess the monitor's report.

Research monitors are required to promptly report their medical monitoring and oversight monitoring observations and findings to the IRB or other designated official.

Data Collection Sheets

See attached Excel spreadsheet.

Objectives:

The obstetrics literature to date focuses on TXA use prior to non-emergent cesarean delivery or in response to hemorrhage. Data is lacking in the area of prophylactic use prior to vaginal delivery. The aim of this study will be to assess the ability of TXA to prevent postpartum hemorrhage.

Primary Outcome:

To assess the efficacy of TXA in reducing the incidence of postpartum hemorrhage when given prophylactically prior to all deliveries.

The American Congress of Obstetricians and Gynecologists published 'ReVitalize' in 2014 that defined postpartum hemorrhage as blood loss of ≥ 1000 cc or blood loss accompanied by sign/symptoms of hypovolemia to include blood transfusion within 24 hours following the birth process (includes intrapartum loss).

[figure not shown]
For the purposes of this study, postpartum hemorrhage will be defined as a blood loss of ≥ 1000 cc in addition to all patients requiring blood transfusion (even if blood loss is less than 1000cc).

Secondary outcomes:

Estimated blood loss (EBL) – measured in cubic centimeters. EBL will be decided upon by the delivery provider. All delivering providers at this institution have received formal instruction on estimation of blood loss and a visual aid is available at every bedside and in the operating room (see below).

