Appendix L

Examples of Estimating Blood Loss

Zuckerwise. Estimated Obstetric Blood Loss With Visual Aid. *Obstet Gynecol* 2014.

Delivering providers will also adhere to NAVMEDWESTINST 6320.20, which specifies that once an EBL reaches 500cc, the delivering provider will move from an *estimation* of blood loss to utilizing a *quantitative* blood loss (QBL). QBLs are obtained by the weighing of chux pads, drapes, and linens that have been soiled (after first calibrating the scale to remove the original weight of the contaminated product). It also includes the blood that has been collected in the suction canister in the operating room.

In instances when EBL is decided upon at delivery, and ongoing bleeding occurs after the provider has left the room (and is called back), a QBL should be obtained. The QBL should be added to the initial EBL for a *cumulative* blood loss (CBL).

Percent decrease in hematocrit (Hct) – The percent change of the patients' Hct obtained on admission from that obtained after delivery. A post-operative Hct is routinely obtained six hours following a cesarean delivery. A Hct is not routinely obtained for patients having a vaginal delivery unless EBL exceeds 500cc. A post vaginal delivery Hct will not be obtained in patients for the sole purpose of this research study.

Rates of blood transfusion – The number of patients requiring blood transfusion divided by the total number of deliveries.

The types and amounts of products transfused – in patients requiring transfusion, the type of product (i.e, packed red blood cells, whole blood, fresh frozen plasma, platelets, and cryoprecipitate) will be recorded, along with how many of each type they received.

The use of uterotonic agents – in patients requiring uterotonic agents beyond the first bolus of oxytocin (i.e. second bolus of oxytocin, methylergonovine, 15-methyl Prostaglandin F_{2α}, misoprostol) will be recorded, along with how many doses of each

The need for surgical intervention – the number of patient's that require surgical intervention following a vaginal delivery for the purposes of controlling excessive blood loss divided by the total number of vaginal deliveries

The need for reoperation - the number of patients that require return to the operating room following a cesarean delivery for the purposes of controlling excessive blood loss divided by the total number of cesarean deliveries

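### Blood product amounts and extra uterotonic doses are defined only in women who needed them; a t-test on those subsets is not supported by the planned 890 and can miss or reverse a saving in volume

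*Combined protocol and SAP*

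**What the plan says.** Research Design, d. Statistical Analysis, repeated under Study Procedures, 4. Data Analysis, makes one distributional assumption for everything: "Normal distribution will be assumed given the intended number of patients for analysis". For numeric data the only method is this: "The t-test will be utilized for the comparison of continuous interval data". Categorical data go to chi-square. The same Data Analysis list adds that the secondary outcomes will be tested against institutional rates, estimated by sampling records.

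The Secondary outcomes section defines product amounts "in patients requiring transfusion, the type of product" and uterotonic doses "in patients requiring uterotonic agents beyond the first bolus of oxytocin". Both items say what will be recorded. Neither gives a denominator, an analysis set, a rule for zeros or a named test. By contrast, transfusion, hysterectomy and ICU admission in the same list are each divided by all deliveries.

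The design is single-arm ("c. Methods: One Arm"), and its size was set on the binary primary outcome: "then 890 subjects would need to be recruited to answer the question".

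**The concern.** The large-sample argument is reasonable for a mean over all 890 women. It does not carry over to a mean over a subset when the subset is small and its counts are skewed. Units transfused are such counts: whole numbers, at least 1, with a long upper tail.

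The second problem does not depend on subset size. Whether a woman needs transfusion or another uterotonic is decided after TXA is given and may be changed by it. If TXA keeps milder bleeders out of the subset, those who remain are more severe than the historical users. The two means then describe different kinds of women, and the difference between them is not an effect of TXA on consumption.

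Consumption is part of the study's rationale. The Benefits section cites lower demand for blood products and uterotonics, and Importance to Navy Medicine rests on limited blood bank stock. Total units per delivery addresses that; units per transfused woman does not.

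**Working it through.** **1. The plan's own figure.** Inputs from Statistical Analysis: p0 = 0.0286 and a 50% reduction, so p1 = 0.0143. Alpha and power are not stated; two-sided 0.05 and 80% are assumed. A one-sample test against a fixed rate needs

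n = [1.96·√(p0(1−p0)) + 0.8416·√(p1(1−p1))]² / (p0−p1)² = (0.3267 + 0.0999)² / 0.0143² ≈ 890.

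This matches the plan. One-sided 0.05 with 90% power gives 889, so the plan's settings cannot be recovered uniquely. Either way, 890 was sized for a proportion and says nothing about whether unit or dose counts are close to normal.

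**2. How many women are transfused.** The Primary Outcome section counts every transfused woman as a hemorrhage case, so the transfused cannot outnumber the cases. Expected cases among 890:

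- No effect: 890 × 0.0286 = 25.5 (binomial 95% range 16 to 36)
- Target effect: 890 × 0.0143 = 12.7 (95% range 6 to 20)

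These are ceilings on the expected number transfused. The share of cases transfused is not given. If it is a half or a quarter, the target effect leaves about 6 or 3 transfused women.

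**3. What a t-test on that subset could detect.** For 80% power, normal approximation, the detectable difference is 2.8 × SD × √(1/n1 + 1/n2), assuming a historical sample also of 890 women:

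- 13 against 25: 2.8 × 0.342 = 0.96 SD
- 6 against 13: 2.8 × 0.494 = 1.4 SD

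**4. Uterotonics.** No rate is given, and the definition includes a second oxytocin bolus. Assumed rates of 5%, 10%, 20% and 30% give about 45, 89, 178 and 267 women, or half as many if use is halved. Smallness is therefore not shown here; the selection problem remains.

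**5. Whether selection can hide or reverse a saving.** All distributions below are assumed.

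*Illustration A.* Loss is lognormal (median 350 cc, log SD 0.6); units = 1 + floor((loss − 1500)/400) from 1500 cc upward; TXA multiplies every loss by 0.8; 4 million draws.

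| | Without TXA | With TXA | Change |
|---|---|---|---|
| Units per 1000 women | 11.5 | 3.7 | −68% |
| Transfused per 1000 women | 7.6 | 2.6 | −66% |
| Mean units per transfused woman | 1.51 | 1.42 | −6% |

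*Illustration B.* Units of 1, 2, 3, 4, 6 and 10 have weights 0.25, 0.45, 0.12, 0.08, 0.06 and 0.04. TXA averts half of the 1- and 2-unit transfusions and none of the larger ones. The transfusion rate falls to 0.65 of its former value (−35%). Total units fall from 2.59 to 2.015 per formerly transfused woman (−22%). The mean among those still transfused rises from 2.59 to 2.015/0.65 = 3.10 (+20%).

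*Simulated t-tests.* 890 TXA and 890 historical women; geometric units with mean 2.5; TXA averts half of transfusions; the untreated transfused are 25%, 50% or 100% of hemorrhage cases; 5,000 runs each, leaving out runs where the users-only test could not be computed.

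| | Milder half averted | Random half averted |
|---|---|---|
| Users-only: TXA looks worse | 73–95% | 46–48% |
| Users-only: significantly worse | 16–47% | about 3% |
| Users-only: significant benefit | at most 0.2% | 1–2% |
| All women, zeros included: significant benefit | 3–9% | 7–40% |

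The users-only test almost never finds a saving that exists and, under selective averting, often points the wrong way. The all-women comparison targets the right quantity but has limited power.

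**The case against.** The strongest reply is that the Secondary outcomes items are data-capture wording: a woman who was not transfused has no product type to record, and no test is attached to either item. That stands as far as it goes. A reader might infer that the plan prescribes a comparison confined to users; it does not say so. But these are listed secondary outcomes, the plan commits secondary outcomes to testing, and it offers numeric data only a t-test. Silence on the analysis set leaves the users-only reading as the default.

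Second, a reader might infer that a benefit on transfusion would be lost altogether. It would not. The transfusion rate over all deliveries is a planned outcome, and it falls by 66% in illustration A and 35% in B. What remains exposed is volume, together with the risk of reporting more units per patient beside a lower transfusion rate. Uterotonic use has no stated all-deliveries denominator, so it lacks that safeguard.

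Third, a reader might infer that both subsets are a handful of women. The documents support this only for blood products. Uterotonic users could number in the hundreds, where a large-sample argument may be adequate for the test statistic, though not for the selection.

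Fourth, the illustrations are assumed. A puts 4.0% of untreated women at 1000 cc or more, against the stated 2.86%, and B builds in the selective mechanism. They show that reversal is possible, not that it is likely.

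**Conclusion.** The concern holds in a limited form. The plan does not state the analysis set or method for amounts, its wording points to a users-only t-test, and the normality argument based on 890 does not extend to transfused women: in expectation at most about 25 with no effect and about 13 at the target effect. Those ceilings assume that the institutional 2.86% uses the study's hemorrhage definition, which the documents do not state. For uterotonics the size of the subset is unknown, and the objection there is selection alone. A users-only mean can miss or reverse a saving in volume; how often depends on which cases TXA averts, which the documents cannot tell us. The primary outcome and the yes/no transfusion outcome are unaffected. The change is worth making because volume is part of the stated rationale and the change is small.

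**What to change.** State in the Data Analysis section that the tested outcomes are blood product units per delivery and extra uterotonic doses per delivery, over all women with zeros included. Give the difference from the historical sample with a bootstrap confidence interval. A permutation test is an alternative, but it assumes the two groups are exchangeable, which historical controls do not guarantee. Also report the proportion given any extra uterotonic over all deliveries. Present amounts among users descriptively, without a test.

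For TXA women no new data are needed, since non-users contribute zero. For the comparator, the chart review of the preceding 12 months must extract units and doses woman by woman, with all deliveries as the denominator; the plan now speaks only of estimating rates. Users-only amounts lose their formal test. The interval for product units will be wide because few women contribute non-zero values, and the comparison remains non-randomized.
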